### **2. Study Design**

Include an explanation of the study design (e.g., randomized placebo-controlled, cross-over, cross-sectional, longitudinal, etc.) and, if appropriate, describe stratification/ randomization/blinding scheme.

This is a longitudinal study with matched prospective controls. The patients will undergo treatment and follow-up over the course of 1-7 months. Their results will be compared to that of matched prospective controls with similar treatment and follow duration. There is no placebo, and patients will not be blinded.

Patients will be stratified based on their lesion type and the size of the lesion as these factors may impact the response to laser treatment and thus the data measurements from OCT. Photographs of the patients' treated lesions will be rated for lesion improvement by blinded physicians. OCT measurements of the lesion of interest will be used to validate the improvement and cosmetic results.

Provide precise definitions of the study endpoints and criteria for evaluation; if the primary outcomes are derived from several measurements (i.e., composite variables) or if endpoints are based composite variables, then describe precisely how the composite variables are derived.

Primary endpoints include photographic improvement of the lesion(s) of interest after 1 or more laser treatments. Two board certified dermatologists grade the degree of improvement (clearance of the lesion) in quartiles (no clearance=0-25, mild clearance=26-50, good clearance=51-75, excellent clearance=76-95, complete clearance=96-100). It will be up to the experienced treating dermatologist to determine the number of treatments necessary for maximum clearance of the lesion(s).

Secondary endpoints include measurements with OCT, which show reduced lesion thickness, lesion size, size of blood vessels, and density of blood vessels, and number of superficial blood vessels.

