Some subjects may be asked to participate in more than one imaging session. They will have the option of refusing participation in additional sessions. Follow-up examinations will be performed every 4 weeks. During these examinations, photography and imaging of the lesion of interest will be performed with optional laser treatments to be performed at the discretion of the treating physician and the patient. If no laser treatment is necessary, then the visit should take no more than 30 minutes for a quick follow-up and imaging. Additional laser treatment will require no more than 30 minutes to complete. The number of follow-ups is also determined at the discretion of the treating physician and the patient but could range from 1 to 6 depending on the response of the lesion to treatment.

Matched prospective controls will be gathered to be compared against the imaged, treated, experimental group. The prospective controls will be matched to age, gender, skin type, and type of skin lesion. They will be gathered via a retrospective chart review by abstracting and data directly from our own records.

Describe the duration of a subject's participation in the study. If there are sub-studies, include duration of participation in each sub-study.

For each visit: history and skin examination-30 minutes, imaging – up to 30 mins, and laser treatment – up to 30 mins. These are all maximums and will likely be shorter.

At a follow-up, the patient may or may not receive a laser treatment thus shortening the visit. A patient would be expected to have 1-6 follow ups depending on their response to treatment, so their maximum time in this study could range from about 1 to 6 months. Each follow-up visit is made about 4 weeks from the prior visit.

List data collection instruments (e.g., measures, questionnaires, interview questions, observational tool, etc.).

*Investigator-authored, non-standardized, or un-validated measures must be submitted for review.*

Standardized photography,  
OCT

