##### Statistical Analysis Plan

Primary Objective: The outcome of degree of improvement will be compared between those previous patients that were treated conventionally as a prospective control and those prospective patients who will be treated with assistance from the OCT device. We will use a two-sample t-test to examine the difference in degree of improvement between the two groups at each treatment.

Secondary Objective: We will present the mean/standard deviation and 95% confidence interval of all secondary outcomes (including lesion thickness, size, size of blood vessels, and density of blood vessels, and number of superficial blood vessels.) at each treatment.

2. Describe the primary statistical method(s) that will be used to analyze the primary outcome(s) or endpoints.

N/A

3. Describe the secondary statistical method(s) that will be used to analyze the secondary outcome(s) or endpoints.

N/A

4. If appropriate describe secondary or post hoc analyses of primary outcome(s) or other exploratory analysis.

N/A

5. Sample Size Determination: Explain how the overall target sample size was determined (e.g., power analysis; precision estimation), providing justification of the effect size for the primary outcome based on preliminary data, current knowledge/literature and/or cost consideration; if appropriate, provide sample size justification for secondary outcomes. Power analysis should (at least) match the primary outcome/endpoint.

Literature indicated that laser treatment of skin lesions yields varying degree of clearance across different types of lesions. For example, the Ashinoff et al. 1991 study showed 50% lesion clearance after 3 laser treatments for port wine birthmarks in 12 infants. Another Ashinoff et al. 1991 study showed 70% lesion clearance after 3 laser treatments for capillary hemangiomas in 10 infants. The Clark et al. 2002 study showed 50% lesion clearance after 3 laser treatments for rosacea in 12 adults. Last but not least, the Geronemus 1991 study showed 90% lesion clearance after 1 laser treatment for spider telangiectases in 12 adults. Based on these data, we calculated a mean of 65% ( $\pm 20\%$ ) lesion clearance after 3 laser treatments for any lesion type. Adjusting for the unique characteristics of our patient population at UCI, we estimated a mean lesion clearance of 40% ( $\pm 20\%$ ) after 1 laser treatment for any lesion type.

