The two studies of laser treatment with OCT imaging assistance, Weibel et al. 2016 and Weibel et al. 2018, demonstrated that the depth of lesions and the size and density of the surrounding blood vessels varied widely across patients with burn and traumatic scars and vascular hemangiomas, and that some lesions appearing to be superficial had a much deeper component than could be visualized or palpated. Based on this insight, we hypothesized that laser treatment with imaging assistance would enable dermatologists to calibrate the laser parameters precisely to the actual depth of a lesion and the actual size and density of the surrounding blood vessels; as a result, at least 60% ( $\pm 20\%$ ) of the lesion of any type would be cleared after one laser treatment with imaging assistance as compared to 40% ( $\pm 20\%$ ) without imaging assistance.

A sample size of 34 patients, including 17 patients prospectively treated with laser and imaging assistance for lesions of any type and 17 prospective controls who received laser treatment without imaging assistance, would yield 80% power to test the aforementioned hypothesis using a two-sided two-sample t test at 5% significance level.

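### The primary t-test is repeated at each treatment with no stated analysis set after the first; read naturally, the later tests keep only retreated patients and tend to understate an OCT benefit

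*Combined protocol and SAP*

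**What the plan says.** Section 6, Statistical Considerations, Primary Objective: a two-sample t-test will "examine the difference in degree of improvement between the two groups at each treatment". No analysis set is given for any treatment. The template items on primary, secondary and exploratory methods that follow are marked not applicable, so nothing there fills the gap.

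Section 6, Study Design, defines the primary endpoint as photographic improvement after one or more treatments, with no fixed time point. On the number of treatments it says: "It will be up to the experienced treating dermatologist to determine the number of treatments necessary for maximum clearance of the lesion(s".

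Section 6, Research Procedures, makes laser at the 4-weekly follow-ups optional. It adds that "The number of follow-ups is also determined at the discretion of the treating physician and the patient", ranging from 1 to 6 according to how the lesion responds. Photography and imaging are planned at these follow-ups whether or not laser is given.

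The Sample Size Determination concerns one treatment only. 17 patients per group "would yield 80% power to test the aforementioned hypothesis", "using a two-sided two-sample t test at 5% significance level".

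**The concern.** How many treatments a patient receives is partly a result of how well the earlier ones worked. A test indexed by treatment number, applied to those who received that treatment, therefore conditions on an outcome that follows the intervention. Under the plan's own hypothesis the conditioning is unequal. More OCT patients than controls reach a good result early, so the OCT patients left at treatment 2 are the harder lesions, while the retreated controls still include many that respond well.

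Such a comparison estimates neither the effect of OCT guidance on a treatment session nor its effect over a course of treatment. A real benefit after treatment 1 could be followed by smaller, non-significant differences at treatments 2 and 3 that are read as the benefit fading. All of these tests stand under the primary objective with equal status.

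**Working it through.** **Inputs.** From the Sample Size Determination: OCT mean 60, control mean 40, SD 20 in both groups after one treatment, 17 per group, two-sided 5%, 80% power. The plan gives no clearance level at which treatment stops. I take 50%, 75% and 96% purely as illustrations (96 is the lower bound of the plan's complete-clearance category); none is proposed as a clinical rule.

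**1. The plan's own figure.** Noncentrality = 20 / (20 × √(2/17)) = 2.915 with 32 degrees of freedom. Power from the noncentral t is 80.7% at 17 per group and 78.1% at 16. The planned 17 is reproduced. It applies to everyone after treatment 1.

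**2. Selection alone.** If patients with clearance below c go on to treatment 2, the share continuing is Φ(z), with z = (c − μ)/σ. Their mean treatment-1 clearance is μ − σφ(z)/Φ(z).

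- c = 50: control z = 0.5, share 0.691, mean 40 − 20 × 0.352/0.691 = 29.8. OCT z = −0.5, share 0.309, mean 60 − 20 × 0.352/0.309 = 37.2. Difference 7.4.
- c = 75: shares 0.960 and 0.773, means 38.2 and 52.2. Difference 14.0.
- c = 96: shares 0.997 and 0.964, means 39.8 and 58.4. Difference 18.5.

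The same treatment-1 grades differ by 20 points when everyone is counted.

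**3. Clearance after treatment 2.** Assume each session clears the same fraction s of what remains, so clearance after k sessions is 1 − (1 − s)^k, with s drawn from the planned distributions and limited to 0–0.99. Results by simulation:

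| Treatment stops at | Patients at treatment 2 (OCT / control, of 17 each) | Difference, retreated only | Difference, all patients, last grade carried forward |
|---|---|---|---|
| 50% | 5.2 / 11.8 | about 10 | 13.2 |
| 75% | 13.1 / 16.3 | 16.1 | 17.6 |
| 96% | 16.4 / 17.0 | 19.0 | 19.6 |

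If everyone were retreated, the difference would be 19.7. The last column falls below that because controls who respond less receive more sessions, which is a real consequence of response-driven treatment. The gap between the last two columns is what restricting to retreated patients adds.

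Power at treatment 2, retreated only versus all patients, is about 17% versus 62% when treatment stops at 50%, and about 55% versus 73% at 75%. At treatment 3 with stopping at 75%, about 5 OCT and 12 control patients remain, with a difference of 11.1 against 13.0 points.

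**4. Sensitivity to the model.** If a quarter of lesions gain nothing from OCT guidance, with means and SDs kept close to the plan's, the retreated-only difference at treatment 2 is 1.0 point when treatment stops at 51% and 17.3 at 76%. In the other direction, if clearance is independent from session to session, it is 16.6 points with stopping at 50%.

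**5. Can the sign reverse?** Suppose half the lesions clear 90% per session with OCT and 60% without, and the rest clear 30% in both groups. If treatment stops above 60% and at or below 90%, the retreated OCT patients average 1 − 0.7² = 51% and the retreated controls (84 + 51)/2 = 67.5%. But the treatment-1 SDs are then 30 and 15, not 20 and 20. With stopping at 50% both groups average 51%. With stopping at 96% the result is (99 + 51)/2 = 75% against 67.5%, in favour of OCT. No model tried with SDs near 20 in both groups changed sign.

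**The case against.** The strongest reply is that the plan nowhere restricts the later tests to retreated patients. It leaves the analysis set open, and photographs at follow-ups without laser could supply grades for those who stopped. That stands: the restriction is the natural reading of a test indexed by treatment, not a stated rule. An undefined set for a primary test still has to be settled.

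Second, the study calls itself a pilot, and its one powered comparison, after the first treatment, includes everyone. That also stands and limits the damage. The plan does not, however, name that comparison as the only primary one.

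Third, aiming for the greatest possible clearance suggests that treatment stops late, where the loss is small (19.0 against 19.6 points). This is plausible, but stopping is also left to physician and patient. Patients may stop because of a plateau or by preference, and if poor responders stop, the direction of the bias can change.

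Fourth, Study Design says controls will have similar treatment and follow-up duration. That may bring the numbers closer together, but the patients analysed would still be selected on response. The matching list in Research Procedures does not include number of treatments.

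A reader might also infer that the later tests would turn a real OCT benefit into apparent harm. The documents do not support that: it needs strong differences in effect by lesion type, SDs unlike the planned 20, and a particular range of stopping points.

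**Conclusion.** The concern holds in limited form. The plan tests the primary outcome at each treatment, lets response drive the number of treatments, and does not say who is analysed after the first. If only retreated patients are, the comparisons at treatment 2 and later are selected on response. They will tend to understate an OCT benefit, provided the 60% versus 40% hypothesis is true and good responders are the ones who stop.

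Under the constant-fraction model the added loss at treatment 2 runs from about 3 points, with only about 5 OCT patients against 12 controls, down to 0.6 points, according to a stopping level the plan does not give. Other models widen that range. The first-treatment comparison, with 17 per group and 80.7% power, is untouched. The matter should be corrected, but it does not undermine the study's main planned test.

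**What to change.** In the Primary Objective, name the comparison after the first treatment, in all patients who received it, as the single primary test. This matches the power calculation. State which photograph is graded, since photographs are taken both immediately after laser and at follow-up.

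Do not test on the subset that received a given later treatment. Report those results descriptively, with the number of patients and the number of treatments received by group. Any later between-group comparison should include all first-treated patients, by time since first laser, using the photograph available at that time. Where there is none, use the last graded clearance as a sensitivity analysis.

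The change is to the wording of the analysis plan and leaves treatment decisions as they are. It costs the formal tests of later treatments, which were not powered. Carrying the last grade forward assumes that clearance persists. That assumption may bear real weight, because follow-up is discretionary and controls come from chart review, so later photographs are not assured for patients who stop or for controls.

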### 3. Research Procedures

Provide a detailed chronological description of all research procedures.

A screening log of all potential subjects will be kept at our site. All screening evaluations must be reviewed by the investigator to establish patient eligibility prior to registering the patient for this study.

The following screening evaluation should be completed for all subjects on the first visit:

- Informed consent and photograph release form
- Focused medical history including diagnosis of lesion if applicable. This includes general questioning about the patient's health, well-being, allergies, and medications, and history of the skin lesion in question as identified by the patient and confirmed by the physician.
- Focused skin exam. This includes a detailed medical examination of the skin lesion in question.
- Documentation of area of skin to be studied. This will be determined by the patient's indication and confirmed by the physician.

On visit number one of the study, patients will consent to the study, and an area of skin to be studied will be photographed by digital photography. If the study area is on the face, subjects will be offered to protect their identity.

Non-invasive imaging will then be performed with OCT. Each individual scan with OCT takes about 30 seconds to complete, and we may perform multiple scans on larger lesions. Based on the data and information obtained, the appropriate laser device and settings will be applied for the most optimal treatment to achieve the best results with the fewest side effects. Then laser treatment will be performed on the lesion of interest. Immediate post-treatment imaging and photography will be conducted to assess the results of the treatment. This first visit should take no more than 1.5 hours: approximately 20 minutes for a medical history and focused skin examination, 30 minutes for imaging including photographs, and 30 minutes for laser treatment. These times are all maximums and will likely be shorter. The patient may take as long as needed to consent and is permitted to take the consent form home and return another day to sign and enroll.

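### The secondary endpoint is a reduction in OCT measures, but the planned summary of levels at each treatment gives no confidence interval for that reduction (low severity)

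*Combined protocol and SAP*

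**What the plan says.** The documents describe the OCT outcome in three ways.

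- **Section 1** (outcome variables) calls the secondary outcomes repeat OCT measurements and mentions no change.
- **Section 6, Study Design** frames them as a change: "Secondary endpoints include measurements with OCT, which show reduced lesion thickness, lesion size, size of blood vessels, and density of blood vessels", followed by the number of superficial vessels. It also gives OCT a task: "OCT measurements of the lesion of interest will be used to validate the improvement and cosmetic results".
- **Section 6, Statistical Considerations, item 1** gives the method: "We will present the mean/standard deviation and 95% confidence interval of all secondary outcomes". It then lists the measures themselves, at each treatment. Item 3, which asks for the secondary statistical methods, is answered N/A.

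Research Procedures schedules an OCT scan before the first laser treatment and a second one the same day: "Immediate post-treatment imaging and photography will be conducted to assess the results of the treatment". Follow-up examinations come every 4 weeks: "During these examinations, photography and imaging of the lesion of interest will be performed with optional laser treatments". The number of follow-ups, 1 to 6, depends on the lesion's response and on physician and patient discretion. Study Design likewise leaves the number of treatments to the treating dermatologist. The same part of Research Procedures says "Some subjects may be asked to participate in more than one imaging session" and "They will have the option of refusing participation in additional sessions".

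**The concern.** Section 1 says that the controls have no OCT imaging. Change from the patient's own pre-treatment scan is therefore the only OCT evidence of reduction that the trial can offer. The planned table would show a column of levels, each with its own interval, and no interval for the quantity that Study Design names as the endpoint.

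The plan also leaves three choices open until the data are in hand: which visit-1 scan is the reference, which later scan is compared with it, and which patients enter the comparison. Follow-up scans at visits without laser, including any after the last treatment, have no stated place in a summary made at each treatment.

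**Working it through.** **The plan's own figure.** The only computed design figure is 17 per group for the primary outcome (Section 6, Statistical Considerations, item 5). With a difference of 20 points and ±20% read as an SD of 20, the standardised difference is 20/20 = 1. A two-sided 5% t-test then needs 16.7, rounded up to 17 per group, and has 80.7% power. The figure reproduces, but it does not concern the OCT outcomes, for which no precision is stated.

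**Inputs.** n = 17 imaged patients, the number expected to complete in the study group. The documents give neither an SD nor a within-patient correlation ρ for any OCT measure. Results are therefore in SD units, the SD is assumed equal at the two scans, and ρ is shown as a range.

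**What the planned table yields.** For one mean level, the 95% half-width is t(0.975, 16)/√17 = 2.120/4.123 = 0.51 SD. It does not depend on ρ.

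**What the endpoint needs.** The variance of a within-patient change is s₁² + s₂² − 2ρs₁s₂. The table supplies s₁, s₂ and n but not ρ. With equal SDs the half-width is 2.120 × √(2(1 − ρ)/17):

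| Assumed ρ | Half-width of paired change (SD) |
|---|---|
| 0 | 0.73 |
| 0.5 | 0.51 |
| 0.7 | 0.40 |
| 0.8 | 0.33 |

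**Illustration.** Suppose the table shows a fall of 0.5 SD between two scans in the same 17 patients. At ρ = 0.5 the interval for the change is −0.5 ± 0.514, or −1.01 to +0.01 SD. At ρ = 0.8 it is −0.5 ± 0.325, or −0.83 to −0.17 SD. The same printed means, SDs and intervals fit both results.

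**Who contributes at each treatment.** If the same patients are scanned both times, the difference in means equals the mean within-patient change, and only the interval is missing. This holds for the two visit-1 scans. It largely holds for the first follow-up, if scans without laser are counted. Later, laser is optional, the number of visits depends on response, and imaging can be refused. The patients behind a later mean can then differ from those at visit 1 in a response-related way. Pairing ensures that each comparison uses the same patients, but those who continue remain a selected group. A change score alone does not remove this selection; a time point set in advance for everyone is needed.

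**The case against.** The best defence is that the analysis follows Section 1. The form asks for analysis plans to match that section, and repeat measurements are levels. The phrase in Study Design is loose and mixes an endpoint with a hoped-for result, and the reference to all secondary outcomes might silently include reductions. This stands in part: the documents hold two descriptions, and the mismatch is with Study Design. It does not settle the matter, because Study Design is where endpoints are to be defined precisely and where OCT is asked to validate improvement. The analysis text lists the raw measures and names no reference scan.

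It is also fair to say that the summary is descriptive, the study is a pilot, and a paired interval could be computed later from scans already planned. That limits the severity. It does not fix the reference scan, time point and patient set before the data are seen.

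Treatment may be a loose word for visit here. The text does not decide it, and the interval for the change is missing on either reading.

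Three stronger readings are not supported:

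- A reader might infer that no baseline is collected. One is: the pre-laser scan at visit 1. Only the analysis text omits it.
- A reader might infer that later means misstate the reduction by a known amount or in a known direction. The documents give no continuation rate, no rule for ending treatment and no link between OCT change and photographic clearance, so neither can be derived.
- A reader might infer that the plan judges reduction by whether the intervals for levels overlap. It states no such rule.

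**Conclusion.** The point holds as a low-severity mismatch between endpoint and analysis. The planned summary gives no interval for the reduction. With 17 pairs, that interval could have a half-width anywhere from 0.73 SD down to 0.33 SD over assumed correlations of 0 to 0.8, and the planned table cannot tell a reader which applies. These figures rest on equal SDs at the two scans, approximate normality and complete pairs; the correlations are assumptions.

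Response-related selection at later treatments is a real possibility under the visit rules, but its size and direction remain unknown. It is a reason to set the time point in advance, and it does not show that the results will be biased.

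**What to change.** In Statistical Considerations, item 1 (Secondary Objective):

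1. Make the main summary the within-patient change in each OCT measure from the visit-1 pre-laser scan to the first 4-week follow-up scan, whether or not laser is given at that visit. Report the paired mean, SD and 95% CI, the number of pairs, and the reasons for missing scans (not asked, refused, could not cooperate).
2. Use absolute change for every measure. Add percent change only where the baseline value is above zero; a count of superficial vessels could be zero, since scars are among the conditions studied.
3. Show changes by lesion-type stratum descriptively, since Study Design stratifies by lesion type and size and a pooled absolute change mixes different conditions.
4. Keep the levels at each treatment as a descriptive listing with n for each. State whether they come from the pre-laser or the post-laser scan.
5. Treat change to the last scan as supportive only, because its timing depends on response.
6. Align the wording of Section 1 and Study Design. Reconcile the two statements in Research Procedures on follow-up imaging, so that it is clear whether the first follow-up scan is offered to everyone.

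**Cost.** A few sentences and a little extra analysis; imaging at the 4-week follow-ups is already described. The downside is that patients without a follow-up scan leave the paired summary. Refusal is allowed, and the inclusion criteria note that children under 4 may have difficulty cooperating. At an assumed correlation of 0.7 the half-width is 0.40 SD with 17 pairs. With 14 pairs it is 2.160 × √(0.6/14) = 0.45 SD, and with 10 pairs 2.262 × √(0.6/10) = 0.55 SD.

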## **SECTION 1: PURPOSE AND BACKGROUND OF THE RESEARCH**

Provide the scientific or scholarly rationale for the research. Describe the relevant background information and the specific gaps in current knowledge that this study intends to address.

The purpose of this research is to assist laser treatment of skin conditions by imaging the skin to obtain information about lesional skin. This is a pilot study that will explore the utility of skin imaging in guiding the laser treatment of skin lesions. This study will utilize Optical Coherence Tomography (OCT). Data acquisition of the skin will guide laser treatment by providing information on skin lesion characteristics.

There have been shown to be many applications for OCT. This imaging modality have been used to examine normal skin, burn scars, hemangiomas, nevus flammeus, fibrosarcomas, rosacea, and telangiectasias. Skin conditions to be studied include vascular lesions, scars, and inflammatory conditions. Normal and lesional skin will be assessed.

Currently, laser settings are selected without the assistance of imaging. Imaging with OCT provides more information about the characteristics of the skin lesion (such as lesion depth, depth of the most superficial part of the lesion, and the size and density of blood vessels), which could allow for more informed selection of laser settings to treat individual skin lesions. OCT has been used to examine laser treatments as well, but our proposed protocol would include the use of OCT to examine the stated skin lesions above before and after laser treatment in order to compare to prospective controls that did not undergo OCT imaging. The goal of our study is to optimize laser treatment with the assistance of OCT and guide future laser treatments. It has been shown that very early treatment of vascular lesions such as Port-Wine birthmark during infancy most often results in a better chance of lesion regression and can greatly improve the clinical and psychosocial well-being of the patient. Therefore, we will utilize OCT imaging, which is FDA-cleared for use on subjects of all ages to image our patient population.

The following imaging modalities will be used:

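### The OCT outcomes are defined as reductions but summarised as raw levels at each treatment, with no change score and no use of lesion type or size

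*Combined protocol and SAP*

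**What the plan says.** All references are to the combined protocol and SAP.

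- **Section 6, Statistical Analysis Plan, Secondary Objective:** "We will present the mean/standard deviation and 95% confidence interval of all secondary outcomes". These are to be given at each treatment. Item 3 of the same section asks the authors to "Describe the secondary statistical method(s) that will be used to analyze the secondary outcome(s) or endpoints" and is answered N/A.
- **Section 6, Study Design:** the secondary endpoints are OCT measurements showing a reduction in thickness, lesion size and the vessel measures. The section also says "Patients will be stratified based on their lesion type and the size of the lesion as these factors may impact the response to laser treatment", continuing "and thus the data measurements from OCT". OCT is meant to corroborate the photographic result.
- **Section 6, Research Procedures:** OCT is done before the first laser treatment and imaging is repeated immediately after it. Follow-up is every 4 weeks, for 1 to 6 visits depending on how the lesion responds. Further laser treatment is discretionary, and patients may decline further imaging sessions.
- **Section 1:** "Skin conditions to be studied include vascular lesions, scars, and inflammatory conditions". Controls have no OCT imaging, so the OCT summaries concern the imaged group alone.

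**The concern.** The endpoint is a change, but the planned summary is a level. To read a reduction from levels, one compares the mean at one treatment with the mean at an earlier one. That works only if the same lesions contribute to both. Here the number of visits depends on response and imaging is optional, so the two means can come from different patients and a different mix of lesion types and sizes. A shift may reflect who is still being imaged, and a real reduction may be hidden or exaggerated.

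The design section names lesion type and size as factors that may matter for the OCT data, but the analysis text never uses them. A raw mean thickness or size across vascular lesions, scars and inflammatory conditions would be hard to interpret for any one of them. At stake is whether the OCT results can corroborate the photographic grading, as the design section intends.

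**Working it through.** **1. The plan's own figure.** The sample size rests on 60% versus 40% clearance with ±20% read as an SD, a standardised difference of 20/20 = 1.0. The exact t calculation gives 16.7, so 17 per group, with power 80.7% at 17. The stated 17 and 80% reproduce. They were set for clearance; no precision is stated for any OCT outcome.

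**2. What a changing mix does to raw means.** Suppose every lesion shrinks by 30% (illustrative). Let R be the mean baseline value among patients still imaged, divided by the mean baseline value of the whole group. The ratio of raw means is 0.70 × R.

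| R | 0.70 × R | Apparent reduction |
|---|---|---|
| 0.90 | 0.63 | 37% |
| 1.00 | 0.70 | 30% |
| 1.10 | 0.77 | 23% |
| 1.20 | 0.84 | 16% |
| 1.36 | 0.95 | 5% |
| 1.43 | 1.00 | 0% |

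The documents do not give R or its direction. The within-patient ratio is 0.70 in every row, because each lesion is compared with itself.

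**3. Interval coverage if a measure is skewed.** The documents give no OCT distribution. The sample-size text says only that lesion depth and vessel measures "varied widely across patients with burn and traumatic scars and vascular hemangiomas", which supports spread but not a particular shape. For assumed log-normal data and n=17, simulated coverage of the t interval is:

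| Log-SD | Middle 90% spans, exp(2 × 1.645 × log-SD) | Coverage of nominal 95% CI | Mean share of total from largest lesion |
|---|---|---|---|
| 0.5 | 5-fold | 93% | 13% |
| 1.0 | 27-fold | 86% | 24% |
| 1.5 | 139-fold | 75% | 35% |

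Equal shares would be 1/17 = 6%. At n=8, which a later treatment could reach, coverage is 91.8% and 83.1% for log-SD 0.5 and 1.0.

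**4. Does mixing types alone spoil coverage?** No. With three equally likely normal types whose means are 1 to 5 within-type SDs apart, coverage at n=17 is 94.8% to 95.1%. With a fixed 6/6/5 composition and spacing of 1 to 3 SDs it is 98.7% to 100%, so the interval is too wide. At spacings of 1, 2 and 3 SDs the raw interval is 1.27, 1.90 and 2.63 times as wide as a type-adjusted one. A rare type (10% of patients) lying 4 or 8 SDs away lowers coverage to 92.9% or 85.1%.

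**5. Precision of the alternatives.** The half-width of a 95% CI in SD units is t(0.975, n−1)/√n.

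- n=17: 2.120/4.123 = 0.51.
- n=6: 2.571/2.449 = 1.05. n=5: 2.776/2.236 = 1.24. These apply if 17 patients split over three types.
- Within-patient change at n=17: √(2(1−r)) × 0.514, which is 0.61, 0.51, 0.40 and 0.23 for a baseline-to-visit correlation r of 0.3, 0.5, 0.7 and 0.9. The change is at least as precise as the level once r reaches 0.5.

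**The case against.** The strongest reply is that these are descriptive secondary summaries in a pilot study, with no OCT test and no OCT data in controls. Little rides on them and the primary comparison is untouched. That stands, and it limits the weight of the point.

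Four stronger readings are tempting, and the documents do not support them.

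- **That the plan states one pooled mean over all lesion types.** It is silent. Pooling is the natural reading of the sentence, but summaries by stratum would also fit the announced stratification. The supportable fault is that the two sections are not connected.
- **That the plan says type and size determine the OCT values.** It says only that "these factors may impact the response to laser treatment and thus the data measurements from OCT".
- **That mixing types makes the 95% intervals fail.** Step 4 shows otherwise. Under-coverage needs marked skew or a rare outlying type. Either is plausible for sizes and counts, but the documents show neither.
- **That repeated scans will be counted as separate observations.** The protocol says "we may perform multiple scans on larger lesions", but nothing makes the scan the unit of analysis. What is missing is a rule for combining scans.

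There is also a fair objection to the remedy. A strict log ratio fails when a value is zero, which can happen for vessel counts and for fully cleared lesions, and so in the best responders. Broad classes such as vascular also leave heterogeneity within them. Both limits shape the fix below.

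**Conclusion.** The point holds as a mismatch between endpoint and summary. The design section defines reductions and flags type and size; the SAP reports levels and uses neither. Because visits depend on response and imaging is optional, successive raw means cannot reliably show reduction. The size of the distortion depends on how the remaining lesions differ at baseline, which is unknown: a true 30% reduction could appear as anything from 37% to none for R between 0.90 and 1.43.

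The coverage problem is secondary and conditional. It is negligible at a 5-fold spread and serious only if a measure spans a range of about 27-fold or more. It should be read as a reason to choose the scale with care, not as a demonstrated failure. Overall this is a modest, inexpensive improvement to descriptive outcomes.

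**What to change.** Revise the Secondary Objective text in the Statistical Analysis Plan, and replace the N/A under item 3, to say:

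1. Each OCT measure is reduced to one value per patient per visit, with a stated rule for combining multiple scans. The baseline is the scan taken before the first laser treatment.
2. The summary at each treatment is the within-patient change from that baseline with a 95% CI. Use a ratio on the log scale for skewed positive measures, and absolute change or median and interquartile range where zeros can occur, including fully cleared lesions.
3. A pooled estimate is adjusted for lesion type, with a descriptive display by type. State whether the size stratum is used.
4. The number of patients contributing is shown at each treatment.

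The cost is wording only; the scans are already planned. There are three downsides. By-type intervals are wide, about 1.05 to 1.24 SD either side at 5 to 6 patients per type, so that display should stay descriptive. If the baseline-to-visit correlation is below 0.5, the change is less precise than the level. And the change score removes differences in baseline mix but not selective dropout: if patients who respond differently stop being imaged, later changes still describe only those who remain, which is why n must be shown.
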